7. INVESTIGATIONAL PLAN

7.1. Overall Study Design and Plan

This is an open-label, dose-escalating, sequential-cohort study assessing the safety, tolerability, immunogenicity, and bioactivity of a single IVT injection of 0.5 mg, 1.0 mg, 2.0 mg and 4.0 mg DE-122 injection administered in a total of approximately 12 subjects with refractory exudative AMD.

Approximately 12 subjects in four cohorts (2 or 3 subjects in Cohort 1, 3 subjects each in Cohorts 2, 3 and 4) will receive a single IVT injection of DE-122 in the study eye. Decisions regarding dose escalation will be based on the recommendations of the Safety Review Team consisting of an external Retina Specialist, the Medical Monitor, and the Drug Safety Physician. Dose-Limiting Toxicity response observed in any cohort will result in termination of the dose escalation.

The study is designed to include up to a 7-day screening phase and 90-day treatment/follow-up phase for each subject.

The first eligible subject in Cohort 1 will receive a single intravitreal injection of 0.5 mg DE-122 in the study eye and will be evaluated through Visit 3 (Day 8±1). The Safety Review Team will review the safety parameters and determine if the safety and tolerability are acceptable.

If acceptable, up to two additional eligible subjects in Cohort 1 will each receive a single intravitreal injection of 0.5 mg DE-122 in the study eye before starting Cohort 2. After the first 2 or 3 subjects in Cohort 1 have completed Visit 5 (Day 30±2), the Safety Review Team will review the safety parameters of the first 2 subjects in Cohort 1 and determine if the next dose (1.0 mg) will be administered to Cohort 2.

The same enrollment procedures will be followed for Cohort 2 (1.0 mg of DE-122), Cohort 3 (2.0 mg of DE-122) and Cohort 4 (4.0 mg of DE-122), however 3 subjects must be enrolled in these cohorts.

Rescue therapy with anti-VEGF medication may be allowed at Visit 3 (Day 8±1) and/or at Visit 7 (Day 60±3) provided the following rescue criteria are met: < 5 letters gained from baseline BCVA or < 50 microns reduction from baseline CST as measured by SD-OCT.

All subjects will receive IVT anti-VEGF treatment at Visit 5 (Day 30±2) after DE-122 IVT injection, in order to avoid a prolonged period without treatment, if no rescue therapy was given at Visit 3 (Day 8±1), regardless of the visual acuity and CST outcomes.

[figure not shown]

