7.4. Dose Adjustment Criteria

The Safety Review Team will review safety parameters after the first subject in a given cohort has completed Visit 3 (Day 8±1). The remaining subjects in the cohort will receive the same dose if neither the safety criteria for adjusting or stopping doses ([Section 7.4.1](#)) nor the criteria for study termination ([Section 7.5](#)) preclude their treatment.

When the first 2 or 3 subjects in Cohort 1 and 3 subjects in other Cohorts have completed Visit 5 (Day 30±2), the Safety Review Team will again evaluate the safety parameters. If the safety criteria for adjusting or stopping doses and the criteria for study termination are not met, the first subject in the next cohort will receive the next higher DE-122 dose level.

The same safety evaluations will be performed for each cohort.

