7.4.1. Safety Criteria for Adjusting or Stopping Doses

If more than one of the following dose limiting toxicities is observed in any one cohort, planned doses may be adjusted or stopped by the Safety Review Team.

- Visual acuity loss from baseline defined as:
 - Loss of best corrected visual acuity (BCVA) of 30 or more letters not due to vitreous hemorrhage or injection procedure **OR**
 - Transition to no light perception (NLP) not due to injection procedure
- Clinically significant inflammation defined as:
 - > 3+ vitreous haze as measured by the National Eye Institute Grading Scheme ([Nussenblatt et al., 1985](#)) **OR**
 - Sterile endophthalmitis (including the presence of hypopyon)
- Severe IOP elevation as measured by tonometry, on two separate exams, at least one day apart, excluding day of injection (despite pharmaceutical intervention):
 - > 35 mmHg **OR**
 - Increase of > 15 mmHg from baseline

If any of the following adverse events (AEs) occur in any one subject in any cohort, planned doses will be adjusted by treating additional subjects at the same or lower dose level (the occurrence of a second adverse event in either the same or different subjects in one cohort will qualify for study termination, [Section 7.5](#)):

- Retinal non-perfusion of the study eye/vascular occlusion
- Vasculitis
- Retinitis
- > 2+ disc edema
- > 2 quadrants of retinal hemorrhage

If there is insufficient safety information in a given cohort at any time, the Safety Review Team may determine to treat additional subjects within that cohort before moving to the next cohort.

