8.1. Subject Inclusion Criteria

At Screening (Day -7 to Day -1) and Visit 1 (Day 1), subjects must meet all of the following inclusion criteria:

1. Provide signed written informed consent on the IRB / EC approved ICF and provide authorization as appropriate for local privacy regulations.
2. Male or female 50 years of age or older on the date of signing the ICF and able and willing to comply with all treatment and follow-up study procedures.
3. Diagnosis of subretinal or intraretinal fluid secondary to exudative AMD as assessed by SD-OCT in the study eye with a minimum of 300 μm in the central subfield.
4. Prior treatment in the study eye with any intravitreal anti-VEGF medication within the past one year prior to Screening visit (at least 3 anti-VEGF treatments within 6 months or 6 anti-VEGF treatments within 12 months).
5. Treatment with intravitreal injection of anti-VEGF > 30 days and < 60 days from Visit 1 (Day 1).
6. Clinical examination or imaging shows persistent or increasing lesion activity (intraretinal or subretinal fluid, exudation, or hemorrhage) despite continuous anti-VEGF therapy.
7. Total lesion size of ≤ 12 disc areas, contain $\leq 50\%$ hemorrhage and $\leq 50\%$ fibrosis and $\leq 50\%$ retinal pigment epithelial atrophy in the study eye.
8. BCVA of 65 to 20 ETDRS letters (20/50 to 20/400) in the study eye.
9. Fellow eye must have BCVA equal to or better than the study eye, but not worse than 35 ETDRS letters (20/200)
10. Reasonably clear media and some fixation in the study eye to allow for good quality SD-OCT and fundus photography.

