11.2.4. Best Corrected Visual Acuity

The BCVA will be recorded using the ETDRS chart and total number of letters at 4 meters and 1 meter will be recorded at each visit. If a subject could not read ETDRS chart, Finger Counts, Hand Motion, Light Perception, or No Light Perception will be recorded.

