4.3.2. Safety Measures

[Table 2](#) below lists the safety measures to be evaluated in this study.

Table 2: Safety Measures

Safety Measure	Note
Best-corrected visual acuity	BCVA measures the acuteness or clearness of the best-corrected vision, with a range of [0, 97] in ETDRS letters. An increase in BCVA indicates an improvement in the best-corrected vision.
Slit-lamp biomicroscopy findings: lid Redness, lid edema, conjunctival hyperemia, conjunctival Edema, corneal edema, anterior chamber cells, anterior chamber flare	Anterior Chamber Cells will be graded as 0 = No cells, 0.5 = 1-5 cells, 1 = 6-15 cells, 2 = 16-25 cells, 3 = 26-50 cells, or 4 = >50 cells. Anterior Chamber Flare will be graded as 0 = None, 1 = Faint, 2 = Moderate, 3 = Marked, or 4 = Intense. The other six biomicroscopy parameters will be graded as 0 = None, 1 = Mild, 2 = Moderate, or 3 = Severe.
Iris	The iris status of an eye will be graded as either Normal or Abnormal.
Lens description	The lens of an eye will be classified as phakic, aphakic, or pseudophakic.
Phakic lens severity score	The status of a phakic lens will be graded as 0 = None, 1 = Mild, 2 = Moderate, or 3 = Severe.
Intraocular pressure	IOP, the fluid pressure inside the eye, is recorded in mmHg. The IOP of an eye is derived as the mean/median of two or three consecutive IOP measurements. In this study, the IOP increase of ≥ 10 mmHg from baseline needs to be reported as an AE.

Table 2: Safety Measures (Continued)

Indirect Ophthalmoscopy findings: cup/disc ratio, retina, macula and choroid, vitreous	Cup/disc ratio will be recorded with two decimal points (e.g., 0.80). Retina (including macular) and choroid will be graded as either Normal or Abnormal. Vitreous haze will be graded as: 0 = Clear, Trace or 0.5+ = Trace, 1+ = Few opacities, mild blurring, 2+ = Significant blurring but still visible, 3+ = Optic nerve visible, no vessels seen, and 4+ = Dense opacity obscures the optic nerve head.
Fundus Photography	Optic disc, Macula.
Fluorescein Angiography	Optic disc, Macula.
Laboratory assessments: hematology, chemistry and urinalysis	Refer to Section 21.4.15 of the protocol for the list of the minimum blood parameters and urine parameters.

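### The 30-letter visual-acuity DLT cannot be met by a study eye that enters with 20 to 29 letters; for these eyes acuity loss alone is a DLT only at no light perception

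*Protocol*

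**What the plan says.** Protocol 7.4.1 defines the visual-acuity DLT as a change from baseline that meets either of two limbs. The first is a letter loss: "Loss of best corrected visual acuity (BCVA) of 30 or more letters not due to vitreous hemorrhage or injection procedure". The second covers an eye that loses all sight: "Transition to no light perception (NLP) not due to injection procedure".

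Protocol 8.1, item 8, sets the entry range: "BCVA of 65 to 20 ETDRS letters (20/50 to 20/400) in the study eye". The inclusion criteria apply at both Screening and Visit 1, and Protocol 13.1 takes the last pre-injection value as baseline, so a baseline of 20 to 29 letters is permitted. SAP 4.3.2, Table 2, describes BCVA as a score "with a range of [0, 97] in ETDRS letters". For eyes that cannot manage the chart, Protocol 11.2.4 says: "If a subject could not read ETDRS chart, Finger Counts, Hand Motion, Light Perception, or No Light Perception will be recorded". Neither document gives these grades a letter value.

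Two statements govern what follows a DLT. Protocol 7.1 says: "Dose-Limiting Toxicity response observed in any cohort will result in termination of the dose escalation". Protocol 7.4.1 says: "If more than one of the following dose limiting toxicities is observed in any one cohort, planned doses may be adjusted or stopped", and gives that decision to the Safety Review Team. Under Protocol 7.4, if the criteria in 7.4.1 and 7.5 are not met, "the first subject in the next cohort will receive the next higher DE-122 dose level".

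**The concern.** A fixed loss of 30 letters works only if the eye has 30 letters to lose, and the entry range begins 10 letters below that. In the lowest part of the range the first limb has no effect, which leaves only no light perception. Between the two lies near-total loss of vision: 0 letters, finger counts, hand motion and light perception. An eye that goes from 30 letters to 0 has a DLT; an eye that goes from 29 letters to hand motion does not.

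Safety and tolerability are the primary objective, and each cohort has two or three subjects, so the classification of one subject can decide what happens next. These eyes are within the intended population: 20 letters is an explicit bound, and the study eye is by rule the worse-seeing eye. The criterion also reaches beyond escalation. Protocol 7.4 uses 7.4.1 after the first subject's Day 8 visit to decide whether the rest of the cohort receives the same dose.

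**Working it through.** The plan states no figure for this point, so there is none to reproduce. The check is direct arithmetic.

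**Inputs**

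- Letter limb of the DLT: loss of at least 30 letters from baseline (Protocol 7.4.1).
- Admissible baseline in the study eye: 20 to 65 letters (Protocol 8.1, item 8).
- Lowest possible letter score: 0 (SAP 4.3.2, Table 2).

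**Step 1: can the limb be reached?** The largest measurable loss is baseline − 0. The score needed to meet the limb is baseline − 30 or lower.

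| Baseline (letters) | Largest loss | Score needed for the DLT | Reachable? | Shortfall from 30 |
|---|---|---|---|---|
| 20 | 20 | −10 or lower | no | 10 |
| 25 | 25 | −5 or lower | no | 5 |
| 29 | 29 | −1 or lower | no | 1 |
| 30 | 30 | 0 | yes, only at 0 | none |
| 35 | 35 | 5 or lower | yes | none |
| 65 | 65 | 35 or lower | yes | none |

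**Step 2: how much of the range is affected?** Counting whole-letter scores:

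- Admissible baselines: 65 − 20 + 1 = 46.
- Limb out of reach (20 to 29): 29 − 20 + 1 = 10, and 10/46 = 21.7%.
- A fall to 0 is a DLT (30 to 65): 65 − 30 + 1 = 36, and 36/46 = 78.3%.

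**Step 3: do the off-chart grades help?** Scored as 0 letters, they give the same losses as in Step 1, so the limb stays out of reach. They would need negative values (−1 at a baseline of 29, −10 at a baseline of 20), and these lie outside the SAP's range.

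**Step 4: what changes under each decision rule?** Take a fall to 0 letters from a baseline of 20 to 29, with no other qualifying event in that eye.

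| Rule | Situation | DLTs as written | DLTs if the fall counted | Threshold |
|---|---|---|---|---|
| Protocol 7.1 | this loss alone | 0 | 1 | any DLT; escalation ends |
| Protocol 7.4.1 | this loss plus one other DLT in the cohort | 1 | 2 | more than one; the team may adjust or stop doses |

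Under either rule the classification of this one eye decides whether the threshold is crossed.

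**The case against.** The arithmetic is not in dispute. The case against concerns consequence and cost.

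*The two decision rules do not agree.* Protocol 7.1 makes any DLT end escalation, whereas 7.4.1 asks for more than one in a cohort and then only permits action. If 7.4.1 governs, a lone fall to 0 letters would trigger nothing even after the repair. This stands as a limit on the size of the consequence. It does not remove the defect, because the eye is misclassified under both rules.

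*Human oversight covers much of the risk.* Escalation rests on the Safety Review Team's recommendation. The team looks at the first subject of each cohort after Day 8 and at the cohort after Day 30. BCVA is measured at every visit and is a listed safety parameter. The signals in Protocol 7.5 are not presented as a complete list. A sight-threatening event is a serious adverse event with its form due within 24 hours. Inflammation, pressure rises and the listed retinal events have their own rules. All of this is true, and escalation after such a loss would not be automatic. It still leaves these eyes to judgement where eyes entering at 30 letters or more have a written criterion.

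*The acuity procedure sits in a Study Procedures manual that was not available for this review.* A manual could rescue the limb only with negative letter values, which would contradict the SAP's range.

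*The repair could stop escalation because of disease.* The limb does not require attribution to DE-122. Subjects have persistent or increasing lesion activity, and those not rescued at Day 8 wait until Day 30 for anti-VEGF treatment. If 7.1 governs, one disease-related 20-letter loss from a baseline of 20 would end escalation. That is a fair caution, but the limb already carries this risk for every eye it can reach.

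*Few subjects remain.* Two Cohort 1 subjects had finished without adverse events by June 2016, which leaves three in each of Cohorts 2 to 4 and possibly one more in Cohort 1. These cohorts include all the higher doses, where the criterion matters most.

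**Conclusion.** The concern holds. For a baseline of 20 to 29 letters, 10 of the 46 admissible scores, the letter limb is out of reach by 1 to 10 letters, and acuity loss alone is a DLT only at no light perception. The boundary is exact: an eye at 30 letters can just meet the limb by falling to 0.

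The result rests on the SAP's floor of 0 letters and on the absence, in both documents, of a letter value for the off-chart grades. The 22% describes scores, not subjects. The documents give neither the share of subjects who will enter in this range nor the chance of such a loss, and none is estimated here. In practice, withholding escalation for acuity loss in these eyes depends on the team's judgement and not on the written criterion. The change should be made. Confidence is high on the text of the two documents.

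**What to change.** Amend the first acuity limb in Protocol 7.4.1 so that it reads, in substance:

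> Loss of 30 or more letters or, for a baseline below 30 letters, a fall to 0 letters or to finger counts, hand motion or light perception.

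Keep the present exclusions for vitreous hemorrhage and the injection procedure, and state that off-chart grades count as 0 letters for the DLT. A fall to 0 letters would then count at 46 of 46 admissible baselines, up from 36. The SAP does not need to change.

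The cost is one protocol amendment with IRB or IEC re-approval (Protocol 17.1). No new data are needed, since BCVA is measured at every visit and off-chart grades are already recorded. The criterion becomes somewhat more sensitive at low baselines: a 20-letter loss would count at a baseline of 20, while a 29-letter loss at a baseline of 30 or more still would not. With that comes some added chance of a DLT caused by disease progression in these eyes.

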7.5. Criteria for Study Termination

Unacceptable safety signals that prevent moving to the next higher dose cohort or result in stopping the study may include any of the following, if deemed to be related to study drug DE-122 (not DE-122 administration procedures):

- Pattern of systemic AEs
- Any of the following AEs in any 2 subjects in any cohort:
 - Retinal Non-perfusion of the study eye/vascular occlusion
 - Vasculitis
 - Retinitis
 - > 2+ disc edema
 - > 2 quadrants of retinal hemorrhage

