11.1.3. Events of Special Interest

Events of Special Interest (ESIs) are events that may require special attention for the purposes of on-going patient safety review during this study. The following are considered ESIs and should be reported on the appropriate eCRF with as much information as available within 24 hours of knowledge of the event:

- **Study medication administration error** – Study medication administration errors determined to be significant by the Clinical Investigator will be reported and evaluated as ESIs. Examples of study medication administration errors may include, but are not limited to: overdose of study medication and administration of study medication from an incorrect kit.
- **Pregnancy** - There are no controlled data with the investigational product in human pregnancy. It is required that women of childbearing potential use effective contraception during the study and recommended for 12 weeks after the completion of the study. Any pregnancy occurring during study treatment should be reported and the subject removed from the study. The subject should be followed until the end of pregnancy or until the end of the study, whichever is longer.
- **Ocular telangiectasia and bleeding** – There is no data showing that the investigational product is related to these events. However, these are seen in the Osler-Weber-Rendu (OWR) syndrome, a genetic condition that causes endoglin dysfunction. DE-122 binds to and suppresses human endoglin, thus information about the ocular manifestations of OWR are of value in predicting possible ocular adverse following IVT injection of DE-122. Any ocular telangiectasia or bleeding (both extra and intraocular) occurring during study treatment should be reported and the subject followed until the end of the study or resolution of the event.

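### The 30-letter acuity DLT in Protocol 7.4.1 leaves out losses from any vitreous hemorrhage, so one caused by DE-122 does not count under that limb (narrow gap, minor severity)

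*Protocol*

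**What the plan says.** Section 7.4.1 has two acuity limbs. The first is "Loss of best corrected visual acuity (BCVA) of 30 or more letters not due to vitreous hemorrhage or injection procedure". The second is "Transition to no light perception (NLP) not due to injection procedure". If a cohort has more than one DLT, "planned doses may be adjusted or stopped by the Safety Review Team".

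Section 7.4.1 also has a separate list of ocular adverse events, any one of which requires dose adjustment. It names retinal hemorrhage in more than two quadrants but not vitreous hemorrhage. The termination list in 7.5 names the same ocular events, requires relatedness to DE-122, and is open-ended: "Unacceptable safety signals that prevent moving to the next higher dose cohort or result in stopping the study may include any of the following".

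Under 7.4, if the criteria in 7.4.1 and 7.5 are not met after Day 30, "the first subject in the next cohort will receive the next higher DE-122 dose level". Section 7.1 bases escalation on the Safety Review Team's recommendations and also states: "Dose-Limiting Toxicity response observed in any cohort will result in termination of the dose escalation".

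Section 11.1.3 makes ocular bleeding, inside or outside the eye, an event of special interest to be reported within 24 hours. Its reason is mechanistic: "DE-122 binds to and suppresses human endoglin, thus information about the ocular manifestations of OWR are of value in predicting possible ocular adverse" events. It also says of ocular telangiectasia and bleeding: "There is no data showing that the investigational product is related to these events". It attaches no dose action. The SAP repeats the 7.1 sentence in its section 3.1 and does not define or modify the DLT.

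**The concern.** Excluding hemorrhage that the disease itself produces is sensible, since section 5 lists vitreous hemorrhage among the complications of exudative AMD. But the wording removes vitreous hemorrhage of every cause. That includes a bleed the investigator attributes to DE-122, and intraocular bleeding falls within the ocular event the protocol singles out on the drug's mechanism.

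The two acuity limbs also disagree. A vitreous bleed that ends in NLP counts. The same bleed costing, say, 35 letters short of NLP does not. No reason is given for the difference.

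Safety by dose level is the primary objective. The DLT criteria are the written test that decides whether the default to escalate applies. An event left out of them adds nothing to that test, however many subjects in a cohort have it.

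**Working it through.** The documents give no DLT rate, stopping probability or error rate, so there is no figure to reproduce. The check compares the text and then counts.

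**1. Scope of the exclusion.** In the 30-letter limb, vitreous hemorrhage and the injection procedure are joined by 'or', and neither is qualified by cause. The authors may have meant only procedure-related hemorrhage, but the text does not say so. The relatedness test in 7.5 governs that section's own list and does not reach the DLT definition. The exclusion covers losses *due to* the hemorrhage. A 30-letter loss from another cause, in an eye that also has a bleed, still counts.

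**2. What must hold for a related bleed to escape every written trigger.**
- It costs 30 or more letters without reaching NLP.
- Vitreous haze is 3+ or less. Of the six grades in 21.4.8 (0, 0.5+, 1+, 2+, 3+, 4+), only 4+ exceeds 3+.
- There is no sterile endophthalmitis and no qualifying IOP elevation.
- There is no retinal non-perfusion or vascular occlusion, vasculitis, retinitis, disc edema above 2+, or retinal hemorrhage in more than two quadrants.

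**3. Baselines at which it can arise.** Eligible acuity is 20 to 65 letters (8.1), which is 65 − 20 + 1 = 46 whole scores. The SAP gives the scale a floor of 0 (4.3.2). Taking off-chart vision as 0 letters (an assumption), a 30-letter loss needs a baseline of at least 30. That leaves 65 − 30 + 1 = 36 scores where it is possible and 46 − 36 = 10 (20 to 29) where it is not. These are scale points, not shares of subjects or measures of risk.

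**4. Counts under each rule, 3-subject cohort, no other DLT.** Two events of the same kind are assumed to satisfy the threshold of more than one in 7.4.1.

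| Related bleeds | DLTs as written | DLTs if reworded | 7.4.1 threshold met, as written / reworded | Literal 7.1 sentence met, as written / reworded |
|---|---|---|---|---|
| 1 | 0 | 1 | no / no | no / yes |
| 2 | 0 | 2 | no / yes | no / yes |
| 3 | 0 | 3 | no / yes | no / yes |

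One related bleed plus one DLT of another kind in the same cohort gives 0 + 1 = 1 as written (not met) and 1 + 1 = 2 if reworded (met).

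**5. Example.** A subject falls from 60 to 25 letters (60 − 25 = 35 lost) from a bleed judged related, with haze 3+ and no NLP. As written this is 0 DLTs. Reworded, it is 1.

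**6. Evidence so far.** Section 5 reports no adverse events in the two Cohort 1 completers. With 0 of 2, the one-sided 95% upper bound on an event rate is 1 − 0.05^(1/2) = 0.78, so this neither supports nor rules out a bleeding risk.

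**The case against.** The strongest reply is that the team does not need the DLT count to act. Section 7.1 bases escalation on the team's recommendations. It has the team judge whether safety is acceptable after the first subject in a cohort, and decide after Day 30 whether the next dose is given. Neither decision is limited to counted DLTs. Section 7.4.1 also lets the team add subjects to a cohort when safety information is insufficient. Even two counted DLTs lead only to a discretionary step. All of this stands. A reader might infer that the team could not stop for such a bleed, or could do so only through the open wording of 7.5. The documents support neither reading.

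A reader might also infer that the event could go unnoticed. It would not. Ocular bleeding is a 24-hour event of special interest, a sight-threatening bleed is an SAE (11.1.2), and acuity and ophthalmoscopy are assessed at every visit. Entry criteria already exclude low platelets, high bleeding risk, and recent hemorrhage or anticoagulant use.

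A third reply is that rewording may catch little. Under 11.1.1.1, an event readily explained by the subject's clinical state does not meet the first ground for a related call, and AMD can explain a vitreous bleed. No known pattern of response to DE-122 has been established for bleeding, and resolution on discontinuation fits a single injection poorly. Many such bleeds could be called not related. This stands as a limit on the gain. It does not justify excluding a bleed that the investigator has judged related.

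Finally, other 7.4.1 criteria also lack a drug-relatedness test. That is true, but there the absence makes the criterion broader. Here it makes the exclusion broader.

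**Conclusion.** The point holds as a narrow gap of minor severity. A loss of 30 or more letters from a DE-122-related vitreous hemorrhage is not counted under the 30-letter limb and, if no other trigger in 7.4.1 or 7.5 is met, adds nothing to the DLT count. The 7.4 default to escalate then stays in place, and holding back depends on the team's discretion. The team has the information and the authority to do so.

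The size is a count, not a probability: 0, 0 and 0 DLTs for one, two or three such bleeds, against 1, 2 and 3 if they counted. At the 7.4.1 threshold the difference appears from two bleeds in one cohort, or from one bleed plus one other DLT.

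The conclusion rests on the plain reading of the limb. It does not depend on any event rate, and it should not be read as evidence that DE-122 causes bleeding: the protocol reports no such data. The difference between 7.1, where any DLT ends escalation, and 7.4.1, where more than one is needed, is a separate matter that this point does not settle.

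**What to change.** Reword the first acuity limb in 7.4.1 to: *Loss of BCVA of 30 or more letters not due to the injection procedure and not due to vitreous hemorrhage judged unrelated to DE-122.* Use the investigator's related / not related call under 11.1.1.1 and the injection-procedure attribution under 11.2.13. Leave the NLP limb and section 7.4 unchanged.

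The cost is one reworded limb, with no new assessment, data field or listing. Disease-driven bleeds judged not related and procedure-related losses stay excluded. The downside is that the call is binary: an ambiguous bleed judged related would count as a DLT and, under the literal sentence in 7.1, a single one could end escalation. In the other direction, bleeds that AMD readily explains would often be judged not related, so the rewording will not capture every drug-related bleed.
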